#### 10.3.5.1 Secondary Safety Endpoints

#### Secondary Safety Endpoint #1: Grade 2 Adverse Events

As with the primary safety endpoint, the adverse events qualifying for this secondary safety endpoint will be determined through adjudication by the CEC. This secondary safety endpoint is based on the occurrence of one or more adverse event as follows, as indicated on the CEC CRF:

- Event is indicated to be a Grade 2 or greater Rectal event lasting at least 5 days through the first 183 days (6 months) or
- Event meets one of the relatedness classifications:
  - Event is indicated to possible, probably, or definitely device-related;
  - Event is related to marking or
  - Event is related to the balloon implantation procedure.

As with the primary safety endpoint, subjects will be counted as having an event if one occurs anytime through Day 183 (6 months) from the marking date or as not having an event if they record no events and are followed through at least Day 169 (6 month minus 14 days) from the marking date. This analysis will be based on the CEC classification as identified in Section 10.3.4.1.1. To compare the event rate of the *ProSpace Group* with that of the *Control Group*, the adverse event endpoint will be analyzed using a Fisher's exact test.

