2.3.3 ADJUSTMENTS FOR MULTIPLICITY

The hypothesis tests for two primary endpoints will be considered independently without adjustment for multiplicity since both tests must reach significance for the study to successfully support the clearance of the balloon device. If both endpoints reach success for the study as outlined below, then three analyses will be performed for consideration in labeling by testing for the superiority of the balloon to the *Control Group*.

- The primary safety endpoint will be evaluated using a two-sided Fisher's Exact test in order to assess superiority of the balloon safety.
- The secondary endpoint rate of Grade 2 or greater rectal adverse events or implantation procedure related adverse events with a duration of at least 5 days will be evaluated using a two-sided Fisher's Exact test.
- The secondary endpoint of the degree of all GU acute toxicity as determined by the Expanded Prostate Cancer Index Composite (EPIC) at the last day of IMRT will be evaluated using a two-sided Rank-Sum (Wilcoxon) test.

The additional endpoints will be evaluated using two-sided tests. If any of these should reach significance at the 0.0167 level, then the results would be considered to be supportive of an additional claim or claims (e.g. a Bonferroni will be used to control for multiplicity).

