2.3.4.5 SECONDARY ENDPOINTS

Secondary Safety endpoints include:

- The rate of Grade 2 or greater rectal or implantation procedure related adverse events with a duration of at least 5 days and implantation procedure related adverse events in the *Balloon Group* subjects compared to *Control Group* subjects in the 6 month follow-up period post marking and/or balloon implantation.
- Degree of all GU acute toxicity as determined by the Expanded Prostate Cancer Index Composite (EPIC).

The adverse event endpoint will be analyzed using a Fisher's Exact test. The EPIC endpoint will be modeled by visit using a repeated measures model with an unstructured covariance matrix.

Secondary efficacy endpoints include:

- Additional dosimetry parameters (D_{Rectum}100, D_{Rectum}90, D_{Rectum}80, D_{Rectum}70) will be evaluated in the balloon arm only, where subjects will serve as their own control (dosimetry reduction after balloon implantation) as the dosimetry parameters are compared to their baseline values per subject.
- Core lab evaluation of distance of rectal wall from the prostate at baseline and last XRT visit. This data will be measured and quantified.

These are all numeric measures and will be compared between groups using Rank-Sum tests.

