## **3.2** Changes to Planned Analyses

Review of the statistical analysis plan identified that windowing is not required to capture events in the first 6 months since the events are classified based on the onset date. Hence, the primary safety analysis would be more accurate if based on events through Day 183 (6 months). The primary safety analysis was updated to reflect this change and the protocol specified cut-off based on 197 days was moved to be a sensitivity analysis. The following changes are reflected in the SAP:

- Section 10.3.4.1.1 now states that the primary safety analysis will include events from marking through Day 183 (6 months). Section 10.3.4.1.3 has been updated to include a sensitivity analysis for the primary safety endpoint from marking through Day 197.
- It has also been clarified in Section 10.3.4.1.3 that the sensitivity analysis using the Kaplan-Meier method will provide estimates for the proportion of subjects experiencing AEs of interest through Day 183.

In addition, Section 10.3.4.1.1 now describes how the primary safety endpoint will be determined through CEC adjudication and clarifies that events related to anesthesia or to the use of a foley catheter will not be considered marking or implantation procedure-related.

It has been clarified in Section 10.3.5.1 that the secondary EPIC safety endpoint will be evaluated for four domains: Urinary Incontinence, Urinary Irritative, Bowel, and Sexual.

Section 10.3.5.2 clarified that the Sign-Rank test would be used for a within-group paired difference comparison.

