### **10.2** Adjustments for Multiplicity of Endpoints

The study has two co-primary endpoints. Each co-primary endpoint will be tested using one-sided alpha equal to 0.025 tests. To control the overall type I error, both co-primary hypotheses must be met to declare success on the primary analysis.

If both co-primary endpoints reach success for the study, then the following three secondary analyses will be performed for consideration in labeling by testing for the superiority of ProSpace to the control:

- The primary safety endpoint will be evaluated using a two-sided Fisher's Exact test in order to assess superiority of ProSpace safety.
- The secondary endpoint rate of Grade 2 or greater rectal adverse events that are also devicerelated, marking/implantation procedure-related, or IMRT-related with a duration of at least 5 days will be evaluated using a two-sided Fisher's Exact test.

The additional endpoints will be evaluated using two-sided tests. The secondary analyses will control for multiplicity to maintain an overall Type I error rate of 0.05. If any of these should reach significance at the 0.0167 level, then the results would be considered supportive of an additional claim or claims (i.e., a Bonferroni will be used to control for multiplicity).

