#### 10.3.4.1 Co-Primary Safety Endpoint and Analysis

#### 10.3.4.1.1 Primary Safety Endpoint

The adverse events qualifying as primary safety events will be determined through adjudication by the CEC. The primary safety endpoint is based on the occurrence of one or more adverse event as follows, as indicated on the CEC CRF:

- Event is indicated to be a Grade 1 or greater rectal event lasting at least 2 days through the first 183 days (6 months) and
- Event meets one of the relatedness classifications:
  - Event is indicated to possible, probably, or definitely device-related;
  - Event is related to marking or
  - Event is related to the balloon implantation procedure.

Note that events related to anesthesia or to the use of a foley catheter will not be considered marking or implantation procedure-related.

Subjects will be counted as having an event if one occurs anytime through Day 183 (6 months) from the marking date or as not having an event if they record no events and are followed through at least Day 169 (6 month minus 14 days) from the marking date. Subjects who terminate the study before Day 169 and did not experience the AE of interest will be considered missing from the PP population and not included in the primary safety analysis. The impact of these subjects will be evaluated in a sensitivity analysis for the primary safety endpoint as described below.

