# 12 List of Tables, Figures and Listings

Tables
Table 14.1.1.1, Study Enrollment, All Subjects
Table 14.1.1.2, Study Enrollment by Site, Intent-to-Treat Population
Table 14.1.1.3, Subject Follow-Up, Per Protocol Population
Table 14.1.1.4, Protocol Deviations, Per-Protocol Population
Table 14.1.2.1, Demographics, Per-Protocol Population
Table 14.1.2.2, Demographics, Intent-to-Treat Population
Table 14.1.3.1, Medical History, Per-Protocol Population
Table 14.1.3.2, Medical History, Intent-to-Treat Population
Table 14.1.3.3.1, Medications at Screening, Per-Protocol Population
Table 14.1.3.3.2, Medications at During Study, Per-Protocol Population
Table 14.1.4.1, Study Procedure Information, Per-Protocol Population
Table 14.1.4.2, Study Procedure Information, Intent-to-Treat Population
Table 14.2.1.1, Primary Analysis of Reduction in V Rectum 70, ProSpace Per-Protocol Population
Table 14.2.1.2, Tipping Point Analysis of Reduction in V Rectum 70, ProSpace Intent-to-Treat Population
Table 14.2.1.3, Covariate Analyses for Reduction in V Rectum 70, ProSpace Per-Protocol Population
Table 14.2.1.4, Summary of Percentage Reduction in V Rectum 70, ProSpace Per-Protocol Population
Table 14.2.1.5, Dosimetry Parameters, ProSpace Per-Protocol Population
Table 14.2.1.6, Rectal Wall Distance, ProSpace Per-Protocol Population
Table 14.2.2.1, Primary Safety Analysis for Occurrence of Grade 1 or Greater Rectal Adverse Events, Per-Protocol
Population
Table 14.2.2.2, Primary Safety Analysis for Occurrence of Grade 1 or Greater Rectal Events Tipping Point
Analysis, Per-Protocol Population
Table 14.2.2.3, Primary Safety Endpoint Cumulative Safety Events by Time Kaplan-Meier Estimates, Per-Protocol
Population
Table 14.2.2.4, Covariate Analyses for Reduction in Primary Safety Endpoint Using Kaplan-Meier Method, Intent-
to-Treat Population
Table 14.2.2.5, Sensitivity Analysis for Occurrence of Grade 1 or Greater Rectal Events through Day 197, Per-
Protocol Population, Per-Protocol Population
Table 14.2.3, Analysis of Grade 2 or Greater Rectal or Procedure-Related Events of Duration of Two or More
Days, Per-Protocol Population
Table 14.2.6.1, Analysis of EPIC Urinary Incontinence Domain Scores by Timepoint, Per-Protocol Population
Table 14.2.6.2, Analysis of EPIC Urinary Incontinence Domain Scores at IMRT Midpoint and Final IMRT Visit,
Per-Protocol Population

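### SAP 10.3.5.1 and 10.2 define the Grade 2 labelling endpoint differently: one also counts any related event of any grade, organ or duration, the other only related Grade 2 or greater rectal events

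*SAP*

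**What the plan says.** SAP 10.3.5.1, under a heading that names Grade 2 adverse events, builds the endpoint from two bullets. The first reads "Event is indicated to be a Grade 2 or greater Rectal event lasting at least 5 days through the first 183 days (6 months) or"; the second reads "Event meets one of the relatedness classifications", followed by three classes: device-related (possible, probable or definite), marking-related and implantation-related. IMRT-relatedness is not among them. The Day 183 counting rule covers both bullets, but the second carries no grade, organ or duration condition.

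SAP 10.2 lists the same endpoint among the superiority tests to be run for labelling once both co-primaries succeed. There it is Grade 2 or greater "rectal adverse events that are also devicerelated, marking/implantation procedure-related, or IMRT-related with a duration of at least 5 days".

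The protocol is worded differently again. Section 2.3.3 has "Grade 2 or greater rectal adverse events or implantation procedure related adverse events with a duration of at least 5 days". Section 2.3.4.5 has "Grade 2 or greater rectal or implantation procedure related adverse events with a duration of at least 5 days and implantation procedure related adverse events". The title of Table 14.2.3 in SAP section 12 refers to "Grade 2 or Greater Rectal or Procedure-Related Events of Duration of Two or More" days.

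SAP 3.2 lists the changes to the planned analyses. Its only entry for 10.3.5.1 is "It has been clarified in Section 10.3.5.1 that the secondary EPIC safety endpoint will be evaluated for four domains".

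**The concern.** One section is a union and the other an intersection, for the same Fisher test. Read literally, 10.3.5.1 makes a man a Grade 2 case because of a brief Grade 1 procedural event outside the rectum. Protocol 2.3.6.1 lists site hematoma and fever as risks of marking or implantation, so such events are expected.

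Device and implantation events arise essentially only in the balloon arm, while marking events can arise in both. The unlimited limb therefore adds cases mainly on one side. It can hide a real reduction in Grade 2 or greater rectal toxicity, or produce a difference between arms that has nothing to do with such toxicity. With two rules standing in the SAP, the choice between them could also be made after the data are seen.

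**Working it through.** **1. The definitions side by side**

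| Source | Rectal limb | Relatedness | Joined by |
|---|---|---|---|
| SAP 10.3.5.1 | Grade ≥2, ≥5 days, any cause | device, marking or implantation; any grade, organ or duration | *or* |
| SAP 10.2 | Grade ≥2, ≥5 days | device, marking/implantation or IMRT | *and* |
| Protocol 2.3.3 | Grade ≥2, ≥5 days | implantation procedure, ≥5 days; unclear whether Grade ≥2 applies | *or* |
| Protocol 2.3.4.5 | as 2.3.3 | as 2.3.3, plus an implantation clause with no grade or duration | *or*, then a trailing *and* |
| SAP Table 14.2.3 title | Grade ≥2, ≥2 days | procedure | *or* |

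Three example subjects show that the definitions give different counts:

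- A brief Grade 1 site hematoma judged implantation-related is a case under 10.3.5.1, not under 10.2, not under Protocol 2.3.3 (too short), and arguably under Protocol 2.3.4.5.
- A Grade 2 rectal event of at least 5 days judged related to nothing in the study is a case under 10.3.5.1 and under the protocol, but not under 10.2.
- A Grade 2 rectal event of at least 5 days related only to IMRT is a case under both SAP sections as they stand. It would drop out if the *or* in 10.3.5.1 were simply changed to *and*, because IMRT is not in its list.

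**2. The plan's own figure**

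The only number attached to this test is its significance level: 0.05 / 3 = 0.01667, which rounds to the stated 0.0167. It reproduces and is not in dispute.

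**3. How far the definition can move the result**

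Inputs from the documents: 136 balloon and 68 control evaluable subjects (Protocol 2.3.4.4, SAP section 6); two-sided Fisher's exact test at 0.0167 (SAP 10.2).

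Inputs assumed: all event rates. The nearest figure is the 5 to 20% and more quoted for late and chronic Grade 2-3 toxicity in the protocol's benefit-risk discussion. The 21% control rate in Protocol 2.3.4.4.2 belongs to the much broader primary endpoint, so 20% is treated as the high end.

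Let *r* be the rate of Grade ≥2 rectal events of at least 5 days, taken as the same under both SAP definitions. Let *e* be the rate of other related events that only 10.3.5.1 counts. With independence, the rate under 10.3.5.1 is 1 − (1 − r)(1 − e). For example, r = 3% and e = 5% give 1 − 0.97 × 0.95 = 7.85%. Power is the sum of the binomial probabilities over all 137 × 69 outcomes where Fisher p ≤ 0.0167 and the balloon rate is the lower.

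Power to show the balloon superior:

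| Rectal rate, balloon / control | 10.2 rule (e = 0) | e = 2%, balloon only | e = 5%, balloon only | e = 5%, both arms |
|---|---|---|---|---|
| 5% / 20% | 78.5% | 59.6% | 32.0% | 57.2% |
| 3% / 15% | 70.4% | 46.5% | 18.7% | 44.7% |
| 3% / 10% | 30.5% | 12.5% | 2.7% | 16.2% |
| 5% / 10% | 12.1% | 4.6% | 0.8% | 7.4% |
| 2% / 5% | 9.2% | 1.5% | 0.1% | 4.0% |

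In the other direction, suppose the rectal rate is the same in both arms, at 5%, 10% or 20%. Added events in a further 5% of balloon subjects only give a significant result against the balloon in 6%, 5% or 3% of trials. A further 10% gives 31%, 19% or 10%.

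**The case against.** The strongest reply is that the *or* is a slip of one word. Section 10.3.5.1 says it works as the primary safety endpoint does and rests on the CEC classification in 10.3.4.1.1. There the first bullet ends "Grade 1 or greater rectal event lasting at least 2 days through the first 183 days (6 months) and", and events related to anesthesia or a foley catheter are excluded from procedure-relatedness. This is good evidence of intent. It does not say which rule governs, though, and changing the one word would still leave 10.3.5.1 without the IMRT class that 10.2 includes. The exclusion, if it carries over, sets no grade, organ or duration limit.

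A second reply is that 10.3.5.1 follows the protocol, which is itself a union and in 2.3.4.5 adds implantation events without limits. Protocol usage (for example the heading of 2.2.6.5) suggests that implantation may include marker placement. That part stands: the implantation limb, and perhaps the marking limb, can be traced to Protocol 2.3.4.5. The device-related class is in neither protocol passage, and 10.2 still contradicts 10.3.5.1.

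A third reply concerns size. The power losses are measured against the narrowest definition. Measured against the protocol's union, part of the loss is procedural harm counted by design, and a repair that keeps the union would not recover it. The rates are assumed and have no source for this endpoint, and the calculation ignores that 10.2 asks for relatedness in the rectal limb while 10.3.5.1 does not. All of this stands. The figures show direction and sensitivity, not an expected loss.

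Finally, the test is run only after both co-primaries succeed, and the main risk is a missed optional claim. That is also true, and it limits how serious the point is.

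**Conclusion.** The point holds. The two SAP sections cannot both be followed, they classify identifiable subjects differently, and the SAP's record of changes does not explain the departure from the protocol. Under the assumed rates, moving from the 10.2 rule to the literal 10.3.5.1 rule takes power from 70–78% to 19–32% when 5% of balloon subjects have additional minor related events, and to 47–60% when 2% do. At a control rate of 5% power starts near 9%, so little can be lost. These figures rest on assumed rates, independence of the two limbs and equal rectal rates under both definitions.

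The literal rule does not make a false claim for the balloon more likely and leaves the co-primary analyses untouched. It should be corrected because the test can support labelling and because the definition must be fixed before results are known.

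**What to change.** Before database lock, remove the unlimited relatedness limb from 10.3.5.1 and use one definition in 10.2, 10.3.5.1 and the title of Table 14.2.3, with a duration of five or more days throughout. Two repairs are open to the sponsor.

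1. **Keep the 10.2 definition.** Change *or* to *and* in 10.3.5.1 and add the IMRT-related class. Justify in SAP 3.2 the narrowing relative to the protocol. Report the Protocol 2.3.3 union beside the tested result, because the narrowing takes low-grade, short or non-rectal implantation events out of the test and so favours the balloon.
2. **Stay with the protocol.** Use the 2.3.3 union with its 5-day duration in both SAP sections. State whether Grade 2 or greater applies to the implantation limb and whether that limb includes marking. This keeps procedural harm in the test but is a less specific measure of rectal toxicity.

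In either case, record the choice in SAP 3.2, together with how the additional implantation clause in Protocol 2.3.4.5 is handled.

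The cost is wording in one or two sections, an entry in 3.2, one table title and, under the first repair, one supportive analysis. No new data are needed: SAP 10.3.6.1 already has the CEC adjudicate device-, procedure-, IMRT- and rectum-relatedness, and 10.3.5.1 already takes grade and duration from the CEC form.

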#### Secondary Safety Endpoint #2: EPIC Scores

An additional secondary safety endpoint concerns the degree of all GU acute toxicity as determined by the Expanded Prostate Cancer Index Composite (EPIC). The version used in this study was the EPIC-26 short form. EPIC scores range from 0 to 100 (transformed from Likert scale responses), with higher scores indicative of better functioning. For each of four EPIC domains (Urinary Incontinence, Urinary Irritative, Bowel, and Sexual), the analysis of the EPIC endpoint will evaluate change in EPIC score over time.

<sup>3 Wei JT, Dunn RL, Litwin MS, Sandler HM, Sanda MG. Development and validation of the expanded prostate cancer index composite (EPIC) for comprehensive assessment of health-related quality of life in men with prostate cancer. Urology. 2000;56(6):899-905.

Statistical Analysis Dlan	Client/Project	BioProtect BP-007
Statistical Allalysis Flan	Version and Date	V2 05-DEC-2021

The domain scores will be summarized descriptively by visit and group along with the change from baseline. Non-parametric Rank-Sum tests will be used to compare change from baseline between groups for each domain at the IMRT midpoint and IMRT final visit.

In addition, for each domain, change from baseline in EPIC score over the course of the study will be evaluated using a mixed model. The independent variables will include visit, treatment group and visitby-treatment group interaction as factors, continuous baseline EPIC score as a covariate and Subject as a random effect. The model will used with an unstructured covariance matrix. In case it fails to converge, a compound symmetry covariance matrix will be used. Least Squares Means will be used to estimate between-group differences for each visit. Type III tests for the factors will be provided.

In addition, change in EPIC score from Screening to the end of IMRT will be analyzed using a separate analysis. The timing of the final IMRT visit is not fixed across subjects, and therefore, cannot be considered as part of the mixed model described above.

This endpoint will be analyzed using the following regression:

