2.2.8 DATA COLLECTION SUMMARY

Time Point	Pre-implantation ¹	Implantation	Post- Implantation ⁴	IMRT ⁵ Treatments	IMRT Follow-up
Informed Consent	X ¹				
Medical History & Physical Examination ¹	X ¹				
AUA Symptom Score	X ¹				
Broad Spectrum Antibiotics	X ²				
Randomization	X ³				
Medications	X ¹			Х	Х
CT as per Section 2.2.4 as indicated ⁶	Х		X	Х	Х
Perineal Healing Status (until healed)				Х	
EPIC Assessment ⁷	Х			Х	Х
Adverse Events		As Needed			
Study Completion/ Termination		As Needed			

Study windows:

- 1. Pre-implantation evaluations.
- 2. Broad-spectrum antibiotics must be started 2 days prior to implantation and continued for a total of 5 days.
- 3. Randomization may occur up to 30 days prior to implantation to allow for facility set up and must occur prior to the pre-implantation CT scan.
- 4. The Post-implantation period begins at discharge from the facility and extends to the first IMRT treatment.
- 5. IMRT treatments must start no more than 24 days after marking/ implantation and data will be collect weekly on the last day of that week's visits.
- 6. CT is taken for the *Balloon Group* up to 30 days pre-implantation and post-implantation, at the last XRT visit and at the 6-month F/U visit. Additionally, CT may be taken in the *Balloon Group* at 12 months if remnants of the balloon remain at 6 months. A CT will be taken in the *Control Group* post-implantation.
- 7. EPIC is taken at baseline, at mid XRT treatment (assuming the treatment plan is for greater than one month) on last XRT day and at every follow-up visit thereafter.

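### The EPIC mixed model in SAP 10.3.5.1 names a redundant subject effect, and its only fallback assumes equal variance at every visit

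*SAP*

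**What the plan says.** SAP 10.3.5.1 (Secondary Safety Endpoint #2) models change from baseline in each of four EPIC domains. On the fixed effects it says "The independent variables will include visit, treatment group and visitby-treatment group interaction as factors", and it completes the model with "continuous baseline EPIC score as a covariate and Subject as a random effect". On the covariance it says "The model will used with an unstructured covariance matrix", followed by "In case it fails to converge, a compound symmetry covariance matrix will be used". The reported result is a set of visit-specific contrasts: "Least Squares Means will be used to estimate between-group differences for each visit".

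The SAP does not say whether the named matrix applies to the residuals, whether the subject effect is dropped under either structure, or whether a robust standard error is used. It prints SAS code for the two co-primary tests but none for this model.

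Protocol 2.3.4.5 is simpler: "The EPIC endpoint will be modeled by visit using a repeated measures model with an unstructured covariance matrix". It mentions no random subject effect and no fallback.

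The mixed model is one of several EPIC analyses. The same SAP section has Rank-Sum tests at the IMRT midpoint and final visit, and a separate regression for change to the end of IMRT. The final IMRT visit is left out because its timing varies and it "cannot be considered as part of the mixed model described above".

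**The concern.** A random subject intercept adds one constant to every element of the within-subject covariance matrix. An unstructured matrix can already absorb that constant, so the data cannot separate the two. The likelihood then has a flat direction, which can cause an optimiser to stop or report a problem for reasons unrelated to the data. Non-convergence is the SAP's only trigger for leaving the unstructured matrix, so a redundant term makes that step more likely than it need be.

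The replacement matters because the model exists to report a group difference at each visit. Homogeneous compound symmetry applies one pooled variance to all visits. If the spread of EPIC change differs between visits, the standard error is too small where the spread is large and too large where it is small. The model is fitted separately for four domains, so different domains could also end with different structures.

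**Working it through.** **Inputs from the documents.** Evaluable subjects: 68 control and 136 balloon (Protocol 2.3.4.4). These agree with the planned enrolment: 204/0.92 = 221.7, rounded up to 222. Drop-out at 6 months: 8% (Protocol 2.3.4.4.2). Two-sided level: 0.05 (SAP 10.1). There is no EPIC power, SD or correlation in either document, so there is no EPIC figure to reproduce.

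**Inputs that are assumptions.** All SDs and correlations, and the use of three post-baseline visits. EPIC is collected at mid-treatment (only if the plan exceeds one month), on the last treatment day, at 6 months and every 6 months thereafter. The last treatment day is outside this model, and visits after 6 months depend on when the last subject finishes, so the documents do not fix the number of visits.

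**Step 1: redundancy.** For T visits the marginal covariance is V = σ_b²J + R, where J is a T × T matrix of ones.

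- *R unstructured.* Replacing (σ_b², R) by (σ_b² − c, R + cJ) leaves V unchanged, so σ_b² is not separately estimable. The count of parameters is T(T+1)/2 + 1, and the rank of the map to V is T(T+1)/2. For T = 2, 3, 4, 5 this is 4, 7, 11, 16 parameters against rank 3, 6, 10, 15.
- *R compound symmetric.* V = σ_b²J + σ_1²J + σ²I, which depends only on σ_b² + σ_1² and σ². That is 3 parameters against rank 2 for any T in this range. The fallback therefore repeats the redundancy if the subject effect stays.

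**Step 2: what the redundancy does to a fit that converges.** REML fits to one simulated data set (68 and 136 subjects, three visits, some drop-out):

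| Model | Subject variance | −2 REML | SEs of the three visit contrasts |
|---|---|---|---|
| Unstructured only | none | 3555.25 | 2.0176, 2.4085, 2.5764 |
| Random intercept + unstructured, three starting values | 0.14, 10.43, 50.90 | 3555.25 each time | within 0.0001 of the line above |
| Compound symmetry only | none | 3590.83 | 2.2666, 2.3236, 2.3986 |
| Random intercept + compound symmetry, two starting values | 7.56, 45.33 | 3590.83 each time | within 0.0001 of the line above |

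In the last row the subject variance and the compound-symmetry covariance add to the same total (7.56 + 101.86 = 109.42; 45.33 + 64.06 = 109.39). Only the split is arbitrary. All these fits reached their optimum.

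**Step 3: size of the test under the fallback.** With complete data, compound symmetry uses the pooled SD at every visit, where pooled SD = √(mean of the visit variances). The SE ratio at visit t is pooled SD / SD_t, and the large-sample two-sided size is 2 × P(Z > 1.96 × ratio). The baseline covariate is left out of this calculation, so the SDs stand for residual SDs of change.

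- SDs 15/15/15: ratio 1.00, size 5.0% at every visit.
- SDs 14/16/17: pooled SD = √((196 + 256 + 289)/3) = √247 = 15.72. Ratios 1.123, 0.982, 0.924; sizes 2.8%, 5.4%, 7.0%.
- SDs 12/16/20: pooled SD = √((144 + 256 + 400)/3) = √266.67 = 16.33. Ratios 1.361, 1.021, 0.816; sizes 0.8%, 4.6%, 11.0%.

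The calculation was repeated with follow-up of 100%, 92% and 50% at the three visits (92% from the planned drop-out, 50% assumed) and with within-subject correlation either exchangeable at 0.5 or autoregressive at 0.5 or 0.8. Ranges over all visits and settings:

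| Assumed SDs | SE ratio | Size of a nominal 5% test |
|---|---|---|
| 15/15/15 | 0.967 to 1.003 | 4.9% to 5.8% |
| 14/16/17 | 0.88 to 1.12 | 2.8% to 8.4% |
| 12/16/20 | 0.75 to 1.36 | 0.8% to 14.0% |
| 20/16/12 | 0.82 to 1.40 | 0.6% to 11.0% |

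**The case against.** The strongest reply is that the redundancy changes nothing that is reported. The contrasts and standard errors depend on V, which is identified, and Step 2 shows them agreeing with the unstructured model alone. That stands. A reader might infer that the whole model is unidentifiable and that failure is built in. Neither follows: only the covariance split is unidentified, the simulated fits reached the same optimum from every start, and failure in practice depends on software and data. Compound symmetry carries the same redundancy, so if redundancy guaranteed failure the fallback would fail as well.

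Second, the phrase about Subject may simply identify the clustering unit, which would make the SAP's first-choice model the protocol's. The absence of code leaves this open. It also means the documents do not establish a departure from the protocol's first-choice model that SAP 3.2 should have listed. The wording still needs correcting, because a programmer following it literally would code both terms.

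Third, the size figures depend on SDs that the documents do not give, and on the fallback being used. A reader might infer that the EPIC standard errors will be wrong. The documents do not support that: with equal SDs and complete data the size is 5.0%.

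Fourth, the consequence is limited. Protocol 2.3.3 bases the EPIC labelling claim on a Rank-Sum test at the last day of IMRT, and no co-primary conclusion uses this model.

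**Conclusion.** The point holds as a specification fault with a conditional consequence. Read literally, the model has one covariance parameter too many under both structures. That does no harm to a converged fit, but it adds an avoidable route to the fallback. The fallback imposes equal variance at all visits without a robust standard error, and can then give tests that are too liberal at some visits and too conservative at others. The illustrative sizes are 5.0% with equal SDs and complete data, 2.8% to 8.4% for a modest spread of SDs (14/16/17), and 0.8% to 14.0% for a wider one (12/16/20). They rest on assumed SDs, correlations and follow-up, three assumed visits and a large-sample approximation. How likely the fallback is cannot be judged from the documents. Because the analysis is secondary and outside the protocol's labelling test, this is worth correcting because it is cheap, not because it threatens the trial's main conclusions.

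**What to change.** In SAP 10.3.5.1:

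- Delete the random subject effect and state the protocol's model: repeated visits within subject, unstructured covariance, fitted by REML. Name Subject as the clustering unit only.
- If that fit does not converge, use heterogeneous Toeplitz, then heterogeneous compound symmetry, in that order.
- Use sandwich standard errors for any structure other than unstructured.
- Kenward-Roger degrees of freedom are a reasonable option for the unstructured fit; leaving them out is not an error.

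The cost is a few words of SAP text and a small change to the code, with no new data or subjects. Removing the subject effect changes no result when the model converges. The small downside is that the standard errors under the revised fallback are estimated slightly less precisely if the visit variances are in fact equal.
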